10.8. Appendix 8: SELENA SLEDAI Disease Assessment Scales

SELENA SLEDAI Score (adapted from [Petri, 2005; Bombardier, 1992]) - Score if descriptor is present at time of visit or in the preceding 10 days.

Wgt.	Descriptor	Definition
8	Seizure	Recent onset (last 10 days). Exclude metabolic, infectious drug cause, or seizure due to past irreversible CNS damage.
8	Psychosis	Altered ability to function in normal activity due to severe disturbance in the perception of reality. Include hallucinations, incoherence, marked loose associations, impoverished thought content, marked illogical thinking, bizarre, disorganized, or catatonic behaviour. Exclude ureaemia and drug causes.
8	Organic Brain Syndrome	Altered mental function with impaired orientation, memory or other intellectual function with rapid onset and fluctuating clinical features. Include clouding of consciousness with reduced capacity to focus and inability to sustain attention to environment, plus at least 2 of the following: perceptual disturbance, incoherent speech, insomnia or daytime drowsiness, or increased or decreased psychomotor activity. Exclude metabolic, infectious or drug causes.
8	Visual Disturbance	Retinal and eye changes of SLE. Include cytoid bodies, retinal haemorrhages, serious exudate of haemorrhage in the choroid, optic neuritis, scleritis or episcleritis. Exclude hypertension, infection, or drug causes.
8	Cranial Nerve Disorder	New onset sensory or motor neuropathy involving cranial nerves. Include vertigo due to lupus.
8	Lupus Headache	Severe persistent headache: may be migrainous, but must be non-responsive to narcotic analgesia.
8	CVA	New onset of CVA(s). Exclude arteriosclerosis or hypertensive causes.
8	Vasculitis	Ulceration, gangrene, tender finger nodules, periungual infarction, splinter haemorrhages, or biopsy or angiogram proof of vasculitis.
4	Arthritis	More than 2 joints with pain & signs of inflammation (ie, tenderness, swelling or effusion).
4	Myositis	Proximal muscle aching/weakness associated with elevated creatine phosphokinase/aldolase or electromyogram changes or a biopsy showing myositis.
4	Urinary Casts	Heme-granular or red blood cell casts.
4	Haematuria	> 5 red blood cells/high power field. Exclude stone, infection, or other causes.
4	Proteinuria	New onset or recent increase of more than 0.5 g/24 hours.
4	Pyuria	> 5 white blood cells/high power field. Exclude infection.
2	Rash	New or ongoing inflammatory lupus rash.
2	Alopecia	New or ongoing abnormal, patchy or diffuse loss of hair due to active lupus.
2	Mucosal Ulcers	New or ongoing oral or nasal ulcerations due to active lupus.
2	Pleurisy	Classic and severe pleuritic chest pain or pleural rub or effusion or new pleural thickening due to lupus.
2	Pericarditis	Classic and severe pericardial pain or rub or effusion, or electrocardiogram confirmation.
2	Low Complement	Decrease in CH50, CC or CC below the lower limit of normal for testing laboratory.
2	Increased DNA Binding	> 25% binding by Farr assay or above normal range for testing laboratory.
1	Fever	> 38°C. Exclude infectious cause.
1	Thrombocytopenia	< 100,000 platelets/mm ³
1	Leukopenia	< 3,000 white blood cells/mm ³ . Exclude drug causes.
TOTAL SCORE		(Sum of weights next to descriptors marked present)

10.9. Appendix 9: SLE Flare Index

(Adapted from [Buyon, 2005; Petri, 2005; Neergaard, 2006; Petri, 1999])

Mild-moderate flare	Severe flare
 Change in SELENA SLEDAI instrument score of 3 points or more (but not to more than 12), or	 Change in SELENA SLEDAI instrument score to greater than 12 ^a , or
 New/worse: Discoid, photosensitive, profundus, cutaneous vasulitis, bullous lupus Nasopharyngeal ulcers Pleuritis Pericarditis Arthritis Fever (SLE) Or	 New/worse: CNS-SLE Vasculitis Nephritis Myositis Plt<60,000 Haemolytic anaemia with Hb<70g/L or decrease in Hb>3 g/L Requiring: double prednisone, or prednisone increase to >0.5mg/kg/day, or hospitalization, or
 Increase in prednisone, but not to >0.5 mg/kg/day, or	 Increase in prednisone to >0.5 mg/kg/day, or
 Added NSAID or hydroxychloroquine for SLE activity, or	 New cyclophosphamide, azathioprine, methotrexate, or mycophenolate for SLE activity, or
 ≥1.0 Increase in PGA score, but not to more than 2.5	 Hospitalisation for SLE activity, or  Increase in a PGA score to ≥2.5

a. Severe flares that are triggered only by an increase in SLEDAI Score to greater than 12 will not be categorised as severe in the analysis.

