12. Have a Grade 3 or greater laboratory abnormality based on the protocol toxicity scale (Section 10.2.1) except for the following that are allowed:

- a) Stable Grade 3 prothrombin time (PT) secondary to warfarin treatment.
- b) Stable Grade 3 partial thromboplastin time (PTT) due to lupus anticoagulant and not related to liver disease or anti-coagulant therapy.
- c) Stable Grade 3 hypoalbuminemia due to lupus nephritis and not related to liver disease or malnutrition.
- d) Any grade proteinuria
- e) Stable Grade 3 gamma glutamyl transferase (GGT) elevation due to lupus hepatitis and not related to alcoholic liver disease, uncontrolled diabetes or viral hepatitis. If present, any abnormalities in the ALT and/or AST must be ≤Grade 2.
- f) Stable Grade 3 neutropenia; or stable Grade 3 lymphopenia; or stable Grade 3 leukopenia, due to SLE

13. Have a history of an anaphylactic reaction to parenteral administration of contrast agents, human or murine proteins or monoclonal antibodies.

14. Have evidence of serious suicide risk including any history of suicidal behaviour in the last 6 months or who in the investigator's judgment, poses a significant suicide risk.

Prior/Concomitant Therapy

15. Have received treatment with belimumab at any time.

16. Have received any of the following within 364 days of Day 0:

- a) Treatment with any B-cell targeted therapy (e.g., rituximab, other anti-CD20 agents, anti-CD22 [epratuzumab], anti-CD52 [alemtuzumab], BLyS-receptor fusion protein [BR3], TACI-Fc)
- b) Abatacept
- c) A biologic investigational agent

17. Have required 3 or more courses of systemic corticosteroids for concomitant conditions (e.g., asthma, atopic dermatitis) within 90 days of Day 0 (Topical or inhaled steroids are permitted).

18. Have received any of the following within 90 days of Day 0:

- a) Anti-Tumour Necrosis Factor (TNF) or anti-IL-6 therapy (e.g., adalimumab, etanercept, infliximab, tofacitinib, certolizumab, golimumab)
- b) Interleukin-1 receptor antagonist (anakinra)
- c) Intravenous immunoglobulin (IVIG)
- d) Plasmapheresis

19. Have received any of the following within 30 days of Day 0:

- a) Intravenous (IV) cyclophosphamide
- b) A non-biologic investigational agent (30 days window OR 5 half-lives, whichever is longer)
- c) Any new immunosuppressive/immunomodulatory agent, anti-malarial, NSAID (See Inclusion Criteria #5)
- d) High dose prednisone or equivalent (>1.5 mg/kg/day) or any intramuscular or intravenous steroid injection

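### Appendix 9 flare index: the haemoglobin fall printed in the severe haemolytic-anaemia item (more than 3 g/L) is out of scale with its 70 g/L alternative, so the number or unit needs checking

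*Protocol*

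**What the plan says.** Protocol Section 9.4.3 lists time to first flare and time to first severe flare over 52 weeks among the secondary endpoints, summarised descriptively. Appendix 9 (Section 10.9) is the table that separates mild-moderate from severe flares.

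In the severe column, one of the new-or-worse manifestations reads "Haemolytic anaemia with Hb<70g/L or decrease in Hb>3 g/L". It counts only with a treatment condition: "Requiring: double prednisone, or prednisone increase to >0.5mg/kg/day, or hospitalization". Several other entries in that column are severe on their own:

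- a prednisone increase above 0.5 mg/kg/day;
- "New cyclophosphamide, azathioprine, methotrexate, or mycophenolate for SLE activity";
- hospitalisation for SLE activity;
- "Increase in a PGA score to ≥2.5".

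The one analysis rule in the appendix, footnote a, says that severe flares "triggered only by an increase in SLEDAI Score to greater than 12 will not be categorised as severe in the analysis". It does not touch the haemoglobin item.

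Two other places give the haemoglobin context. Section 10.2.1 grades haemoglobin in g/dL: Grade 1 from above 9.5 to 11.0, Grade 2 from above 8.0 to 9.5, Grade 3 from 6.5 to 8.0, Grade 4 below 6.5. Section 5.2, exclusion 12, bars participants who "Have a Grade 3 or greater laboratory abnormality based on the protocol toxicity scale". Its only blood-cell-count exception is "Stable Grade 3 neutropenia; or stable Grade 3 lymphopenia; or stable Grade 3 leukopenia, due to SLE", and none of its exceptions covers haemoglobin.

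**The concern.** Two alternatives within one severe item should mark broadly the same degree of severity. Here one limb needs a haemoglobin inside the protocol's Grade 3 band or worse. The other is met by a change of 0.3 g/dL. When one limb is that much easier to meet, the stricter one has almost no work left to do, which suggests that a number or a unit has gone astray.

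At stake is how some flares are labelled. If the intended fall is larger than the printed one, a child with new or worse haemolytic anaemia could be counted as having a severe flare on a trivial haemoglobin change. Time to first severe flare would then be shortened for that child.

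**Working it through.** The plan derives no figure from this item, so there is none to reproduce. The check sets the printed thresholds against the protocol's other haemoglobin figures.

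**Inputs.** Thresholds of 70 g/L and 3 g/L, and the prednisone conditions (Appendix 9). Haemoglobin grade limits (Section 10.2.1). Exclusion 12 (Section 5.2). Entry prednisone of up to 0.5 mg/kg/day (Section 5.1, criterion 5).

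**1. Common unit.** 70 g/L = 7.0 g/dL; 3 g/L = 0.3 g/dL.

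**2. When does the 70 g/L limb add a case?** It needs a current value H < 70 together with a fall R − H of at most 3, where R is the reference value. Then R ≤ H + 3 < 73. The limb adds cases only when the reference is itself below 73 g/L (7.3 g/dL), which is already inside the Grade 3 band or below it. From R of 73 g/L or more, the fall limb contains it entirely.

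**3. Measured from screening.** Exclusion 12 removes Grade 3 or worse, so screening haemoglobin exceeds 8.0 g/dL = 80 g/L. A drop to below 70 g/L is then a fall of more than 80 − 70 = 10 g/L, and 10/3 = 3.3 times the printed threshold. With a screening reference the 70 g/L limb adds no cases.

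**4. Scale of the fall.** Each of Grades 1 to 3 spans 1.5 g/dL = 15 g/L, so 3 g/L is 3/15 = 0.20 of a band. As a share of the reference it is 3/80 = 3.75% at 80 g/L and 3/110 = 2.7% at 110 g/L. From 110 g/L the absolute limb needs a fall of more than 40 g/L, and the other limb only just over 3 g/L. A move from 120 to 116 g/L meets the haemoglobin part while still above the Grade 1 ceiling of 110 g/L.

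**5. When does the number decide the label?** The treatment condition can be met in three ways:

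- Prednisone raised above 0.5 mg/kg/day: severe on its own, whatever the haemoglobin.
- Hospitalisation: severe on its own when it is for SLE activity.
- Prednisone doubled to at most 0.5 mg/kg/day: here the haemoglobin number can decide. With prior dose d above 0, 2d ≤ 0.5 gives d ≤ 0.25 mg/kg/day, the lower half of the range allowed at entry. Section 6.5.1.2 permits increases during the study, so this route is open.

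Even then, no other severe item may be present.

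**6. What else could move?** Any prednisone increase to at most 0.5 mg/kg/day is already a mild-moderate flare in Appendix 9, so the event still counts towards time to first flare. The SELENA SLEDAI in Appendix 8 has no anaemia descriptor, so the primary efficacy endpoint is not affected.

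**The case against.** The strongest reply is that the limbs are joined by *or*, and one limb being broader than the other is overlap rather than contradiction. If the fall is measured from Day 0 or from the previous visit, a child whose haemoglobin is already below 73 g/L can meet the 70 g/L limb without a fall of more than 3 g/L. An absolute floor then does some work in a slow decline. The appendix also describes itself as adapted from published versions, so a departure from them could be deliberate. This stands in part: the text is not logically impossible, and step 3 holds only for a screening reference. It does not explain why a severe item should be met by a fifth of a grade band, and the protocol gives no reason for such a choice.

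The reply is also right that the effect is small. Haemolytic anaemia and a treatment change are still required, and the analysis is descriptive.

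Three stronger readings are tempting and not supported:

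- A reader might infer a g/dL figure left unconverted beside one that was converted, and so a known correct value. The pattern fits, but nothing in the protocol shows the origin or the intended number.
- A reader might take the chance that ordinary variation exceeds 3 g/L as a rate of false severe flares. For a stable patient that chance is 1 − Φ(3/(SD·√2)), or 14% to 36% for an assumed within-person SD of 2 to 6 g/L. The protocol gives no SD, and the figure ignores both the haemolytic-anaemia and the treatment requirements.
- A reader might see a second defect in the lack of a named reference visit. The SLEDAI, PGA and prednisone change items name none either, and this detail is commonly left to the SAP, which is not at hand.

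**Conclusion.** The point holds as a mismatch of scale: on the protocol's own figures, the printed fall of more than 3 g/L is implausible beside the 70 g/L limb, and the number or unit appears wrong. The protocol does not show which value is right, so this is a figure to be checked rather than a proven error with a known correction.

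Its reach is narrow. It can alter only time to first severe flare, and only for new or worse haemolytic anaemia with prednisone doubled to at most 0.5 mg/kg/day and no other severe item met. The documents do not allow a count of participants or events, and nothing here supports saying that severe flares in general are over-called. Sample size is not involved and there is no formal test to affect.

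The conclusion assumes that the unit on the typeset page is g/L in both limbs, as it reads in the copy at hand, and that the treatment condition applies to the haemolytic-anaemia entry. It is worth correcting because the table defines a named endpoint and an unseen SAP would not make the printed scoring table right. Confidence is medium.

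**What to change.** Check the haemoglobin-fall number and its unit against the index version that Appendix 9 cites, and reconcile it with the 70 g/L limb. Correct Appendix 9 and the derivation that rests on it, then apply the reconciled threshold to every participant, including flares already recorded. If the printed figure proves deliberate, say so and give the reason.

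The cost is one number or unit in one appendix, with matching derivation code. Haematology is scheduled at every visit where the flare index is scored (Section 1.2), so no new measurement is needed. How easily recorded flares can be re-derived depends on what the case report form captures, which the protocol does not show.

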6.5.1.2. Steroids

In this section, total systemic steroid dose is defined as the average daily dose of all steroids taken IV, IM, SC, intradermally and orally for both SLE and non-SLE reasons. At Baseline, the average daily dose of steroids is the sum of steroid dose over 7 consecutive days up to, but not including Day 0, divided by 7. While on treatment, the average daily dose of steroids is the sum of steroid dose over any 7 consecutive days divided by 7 in the respective time window.

Systemic Steroids for SLE-related Disease Activity

The total dose of systemic steroids may be increased or decreased as clinically indicated from Day 0 through the 16-week post-treatment follow-up assessment. Treatment of SLE Flares with Steroids: If a participant has an SLE flare requiring an increase in steroid dose the investigator should consider the guidelines prepared for the ACR, for steroid dose/duration of induction therapy [Liang, 2004].

Intra-articular Injections

Participants may receive intraarticular (IA) corticosteroid injections at any time between Day 0 and the 16-week post-treatment follow-up assessment.

Steroids for Reasons Other Than SLE Disease Activity

Inhaled and topical steroids are allowed throughout the course of the study.

Steroids may be given for reasons other than SLE disease activity (such as asthma, contact dermatitis) as clinically indicated.

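### The two stand-alone prednisone items of the flare index are not limited to SLE activity, so a permitted steroid course for another illness is scored as an SLE flare

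*Protocol*

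**What the plan says.** Appendix 9 (section 10.9) has two items in which a prednisone increase alone is enough for a flare. The mild-moderate item reads "Increase in prednisone, but not to >0.5 mg/kg/day, or" and the severe item reads "Increase in prednisone to >0.5 mg/kg/day, or". Neither gives a cause.

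The other stand-alone treatment and hospitalisation items do give one:
- mild-moderate column: "Added NSAID or hydroxychloroquine for SLE activity, or"
- severe column: "New cyclophosphamide, azathioprine, methotrexate, or mycophenolate for SLE activity, or"
- severe column: "Hospitalisation for SLE activity, or"

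The severe column also mentions prednisone inside its new/worse item, but there the increase must accompany a named SLE manifestation.

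Footnote a is the only analysis-level correction: "Severe flares that are triggered only by an increase in SLEDAI Score to greater than 12 will not be categorised as severe in the analysis". It does not reach flares triggered by prednisone.

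On permitted medication, section 6.5.1.2 says: "Steroids may be given for reasons other than SLE disease activity (such as asthma, contact dermatitis) as clinically indicated". Section 6.5 requires the reason for use to be recorded for every medication. Time to first flare and to first severe flare over 52 weeks is a secondary efficacy endpoint (sections 3 and 9.4.3), and the index is scored at Day 0 and at each visit from Week 4 to Week 52 (section 1.2).

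**The concern.** The index is meant to record worsening of lupus. Two of its items respond to any rise in prednisone, while the protocol elsewhere expects some rises to have nothing to do with lupus. Because adjacent rows state the SLE restriction and these two do not, a site can reasonably conclude that the reason for the increase does not matter here.

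A time-to-first-event endpoint is sensitive to this, because one short course for an intercurrent illness fixes the child's event date for good. The study has 65 children and no control arm, so there is no comparator in which the same miscounting would show. Sites may also differ, some scoring literally and others by judgement, and the text does not settle which is right.

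**Working it through.** No sample size or precision figure in the protocol depends on the flare index, so there is no stated figure to reproduce. The check has three steps.

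**1. The items side by side**

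| Appendix 9 item | Column | Cause stated? |
|---|---|---|
| Prednisone rise, not above 0.5 mg/kg/day | Mild-moderate | No |
| Prednisone rise above 0.5 mg/kg/day | Severe | No |
| NSAID or hydroxychloroquine added | Mild-moderate | SLE activity |
| New immunosuppressant | Severe | SLE activity |
| Hospitalisation | Severe | SLE activity |

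Non-SLE systemic steroids are permitted (6.5.1.2), and footnote a removes only severe flares triggered solely by the SLEDAI score. No text says that a non-SLE increase is not a flare. Inhaled, topical and intra-articular steroids would not ordinarily be a prednisone increase, so the issue is confined to systemic courses.

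**2. Which column such a course falls in**

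Let b be the dose before the course, within the 0 to 0.5 mg/kg/day allowed at entry (section 5.1, criterion 5), and let the course add d mg/kg/day for k days. Appendix 9 does not say whether a daily dose or an average is meant, so both are shown.

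- Daily dose: severe if b + d > 0.5. With d = 0.1 this needs b > 0.40. With d = 0.25 it needs b > 0.25. With d = 0.5 or more, any b above 0 is enough.
- 7-day mean: severe if b + d×k/7 > 0.5. With d = 1 for 1 day, b > 0.5 - 1/7 = 0.36. With d = 0.5 for 3 days, b > 0.5 - 1.5/7 = 0.29. With d = 1 for 3 days, b > 0.5 - 3/7 = 0.07. With d = 1 for 5 days, 5/7 = 0.71 already exceeds 0.5.

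If b is assumed uniform on 0 to 0.5, the severe share over courses of 0.1 to 2 mg/kg/day lasting 1 to 7 days runs from about 3% to 100%. The protocol gives no d, k or distribution of b, so the share cannot be fixed.

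**3. Effect on the 52-week flare proportion**

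Let p be the proportion with a true flare by Week 52 and q the proportion with a non-SLE course that meets the item. Both are assumptions, and independence is assumed.

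Counted proportion = 1 - (1-p)(1-q). Overstatement = counted - p = q(1-p).

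| | q = 2% | q = 5% | q = 10% | q = 20% |
|---|---|---|---|---|
| p = 10% | 11.8% | 14.5% | 19.0% | 28.0% |
| p = 20% | 21.6% | 24.0% | 28.0% | 36.0% |
| p = 35% | 36.3% | 38.3% | 41.5% | 48.0% |

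At p = 20% the overstatement is 0.02×0.80 = 1.6 points for q = 2% and 0.10×0.80 = 8 points for q = 10%. Among 65 children that is 65×0.016 = 1.0 and 65×0.08 = 5.2 children. At p = 50% and q = 10% it is 0.10×0.50 = 5 points. The overstatement reaches q itself only if p = 0. A child who has a non-SLE course and later a true flare does not change the 52-week proportion, but the date of first flare moves earlier.

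**The case against.** The best case against the point is that the form is an SLE flare index, listed among the disease activity scales in section 8.2, and that an investigator would not mark an asthma course on it. Its wording is terse throughout: pleuritis, arthritis, low platelets and a rise in PGA carry no SLE qualifier either. Attribution can also be settled in the analysis, from the recorded reason for use, in a plan not shown here. Exclusion 17 removes children who needed three or more systemic steroid courses for concomitant conditions within 90 days, which narrows the exposed group. The endpoint is secondary and descriptive.

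Most of this limits the size and does not remove the gap. Judgement may reduce miscounting, but nothing written requires it, and the restricted neighbouring rows point the other way. Children with one or two earlier courses can still enter, subject to the other criteria. A later derivation rule could repair the result. Even so, the protocol fixes the items that sites score, and its only stated correction addresses a different trigger.

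Three stronger readings are tempting and are not supported:
- *Such flares would usually be severe.* The protocol gives no dose or duration for non-SLE courses, and the severe share depends almost wholly on what is assumed.
- *Treatment of belimumab reactions leaks into efficacy.* For infusion reactions section 6.1 mentions only slowing or interrupting the infusion. Steroid use there would be an inference from the general permission.
- *The flare index is defined on pooled steroid use.* Section 6.5.1.2 does define the total dose as the "average daily dose of all steroids taken IV, IM, SC, intradermally and orally for both SLE and non-SLE reasons", but it limits that definition to its own section and nothing ties it to Appendix 9.

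**Conclusion.** The point holds as a gap in an endpoint definition. As written, a permitted non-SLE systemic steroid course scores as an SLE flare, mild-moderate or severe according to whether the dose passes 0.5 mg/kg/day, and no text in the protocol corrects this. The consequence is confined to time to first flare and first severe flare. No primary endpoint or sample size figure is touched, and there is no formal testing to distort.

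The size is unknown. The q(1-p) range rests on assumed rates, on independence and on sites scoring literally. If sites already apply judgement, the effect is smaller but uneven. The error runs towards more and earlier flares, so it would make the flare result look worse rather than better.

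**What to change.** Either of two changes is enough:
1. Add the words *for SLE activity* to both stand-alone prednisone items in Appendix 9.
2. Leave the items as they are and add a note in the manner of footnote a: a flare triggered only by a prednisone increase whose recorded reason for use is not SLE is not counted as a flare in the analysis.

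In both cases, derive the classification from the reason-for-use field already required by section 6.5, apply it to flares already scored, and report the result as scored alongside.

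The cost is a few words and one derivation from data already collected. There are two downsides. The stated reason of an open-label investigator then decides these cases, as it already does for the neighbouring items, and an error could now favour the drug. Comparability with earlier flare data rests on the result as scored, which is why both should be shown. The change concerns endpoint scoring only and leaves the rules on steroid treatment as they are.

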5.1. Inclusion Criteria

Type of Participant and Disease Characteristics

1. Participants have or have had in series, 4 or more of the American College of Rheumatology (ACR) 11 criteria for the classification of SLE (Section 10.7: [Appendix 7](#)).
2. Participant's age is 5 to 17 years at the time of informed consent.
3. Have active SLE disease defined as a SELENA SLEDAI score ≥ 8 at screening (SELENA SLEDAI scoring see Section 10.8: [Appendix 8](#)).
4. Have unequivocally positive autoantibody test results defined as an ANA titre $\geq 1:80$ and/or a positive [CCI](#) serum antibody test.
5. Are on a stable SLE therapy at Baseline.

The stable treatment at Baseline consists of corticosteroids, anti-malarials, immunosuppressive/immunomodulatory agents and NSAIDs, alone or in combination, at a fixed dose for a period of at least 30 days prior to Day 0.

- a) Corticosteroids (prednisone or prednisone equivalent up to 0.5 mg/kg/day):
 - i. For those participants on alternating day doses of steroids, use the average of 2 daily doses to calculate the average daily steroid dose.
- b) Other immunosuppressive or immunomodulatory agents including methotrexate, azathioprine, leflunomide, mycophenolate (including mycophenolate mofetil, mycophenolate mofetil hydrochloride, and mycophenolate sodium), calcineurin inhibitors (e.g. tacrolimus, cyclosporine), sirolimus, oral cyclophosphamide, 6-mercaptopurine or thalidomide.
- c) Anti-malarials (e.g. hydroxychloroquine, chloroquine, quinacrine)
- d) Non-steroidal anti-inflammatory drugs (NSAIDs)
- e) New SLE therapy must not be added within 30 days of Day 0.

Sex

6. Male and/or female

Contraceptive use by men or women should be consistent with local regulations regarding the methods of contraception for those participating in clinical studies.

Male Participants

No contraceptive measures are required for male participants.

Female participants:

A female participant is eligible to participate if she is not pregnant or breastfeeding, and at least one of the following conditions applies:

- Is not a WOCBP (See Section [10.4, Appendix 4](#))
OR

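### Does footnote a of Appendix 9 drop flares triggered only by a SELENA SLEDAI rise to above 12 from time to first flare?

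*Protocol*

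**What the plan says.** Appendix 9 (Section 10.9) lists flare criteria in two columns. The mild-moderate column includes "Change in SELENA SLEDAI instrument score of 3 points or more (but not to more than 12), or" several other triggers. The severe column includes "Change in SELENA SLEDAI instrument score to greater than 12", with no minimum size of change. Footnote a is attached to that severe row and reads: "Severe flares that are triggered only by an increase in SLEDAI Score to greater than 12 will not be categorised as severe in the analysis".

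Sections 3 and 9.4.3 name time to first flare and time to first severe flare over 52 weeks as a secondary efficacy endpoint. Section 9.4.1 makes every analysis descriptive, with no formal hypothesis test. For the starting level of disease activity, Section 5.1 requires: "Have active SLE disease defined as a SELENA SLEDAI score ≥ 8 at screening".

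Appendix 8 (Section 10.8) gives the descriptor weights. Haematuria (more than "5 red blood cells/high power field. Exclude stone, infection, or other causes") and pyuria (more than "5 white blood cells/high power field. Exclude infection") carry 4 points each. Low complement (a value "below the lower limit of normal for testing laboratory") and increased DNA binding (more than 25% "binding by Farr assay or above normal range for testing laboratory") carry 2 points each.

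**The concern.** The cap at 12 keeps these events out of the mild-moderate row, and the footnote keeps them out of the severe category. If an event must sit in a column to be a flare, a larger rise could be ignored while a smaller one counts. Participants enter with a score of 8 or more, close to the cap, so the gap would lie where this population starts. Two programmers could then derive different event times for a named secondary endpoint.

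Three smaller points in the same table add to the impression of loose drafting:

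- The severe SLEDAI row has no 3-point minimum.
- A PGA rise to exactly 2.5 satisfies both PGA rows.
- The haemoglobin fall in the haemolytic anaemia item (more than 3 g/L) looks small beside the 70 g/L limit in the same line.

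**Working it through.** The protocol gives no figure to reproduce, so this is a logic check of the two SLEDAI rows and the footnote.

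**Rules.** Let s be the reference score and x the new score.

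- Mild-moderate row: x − s ≥ 3 and x ≤ 12, that is 3 ≤ rise ≤ 12 − s.
- Severe row: x > s and x > 12.
- Footnote a: if the severe SLEDAI row is the only trigger, the event is not severe in the analysis.

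**Rises the mild-moderate row accepts.**

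- s = 4: 12 − 4 = 8, so rises of 3 to 8.
- s = 8: 12 − 8 = 4, so rises of 3 or 4.
- s = 9: 12 − 9 = 3, so a rise of 3 only.
- s = 10: 12 − 10 = 2, below the minimum of 3, so none; the same holds for any higher s.

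**Two readings for SLEDAI-only events.** Reading A (literal): an event is a flare only if it still has a column after the footnote. Reading B (label only): the footnote removes the word severe and the event stays a flare.

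| Change | Mild-moderate row | Severe row | First flare, A | First flare, B | First severe flare, A and B |
|---|---|---|---|---|---|
| 8 to 11 | yes | no | yes | yes | no |
| 8 to 12 | yes | no | yes | yes | no |
| 8 to 16 | no | yes | no | yes | no |
| 9 to 13 | no | yes | no | yes | no |
| 10 to 14 | no | yes | no | yes | no |
| 12 to 13 | no | yes | no | yes | no |

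The readings differ only in time to first flare. Time to first severe flare is settled by the footnote under both.

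**Such events are possible.** New low complement plus increased DNA binding adds 2 + 2 = 4, so 10 becomes 14, and Appendix 9 lists neither as a new or worse manifestation. New haematuria plus pyuria adds 4 + 4 = 8, so 8 becomes 16, unless the nephritis item with its treatment or hospitalisation condition, or another row, is also met.

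**Which reading the text supports.** The subject of footnote a is flares, identified as such by the row it is attached to. Its only action is to withhold the severe category, and nothing in Appendix 9 says that the event stops being a flare. Time to first flare carries no severity condition. Reading A also makes 8 to 12 a flare and 8 to 16 not one, a result nobody deriving the endpoint would accept without query. Reading B needs no added rule.

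**The smaller points.**

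- *12 to 13.* The severe row states its criterion, a score above 12. Adding a 3-point minimum would be a design preference, not the repair of an omission.
- *PGA of exactly 2.5.* The mild-moderate row excludes only scores above 2.5, while the severe row starts at 2.5. An event that meets a severe criterion is naturally classed as severe. It is a flare either way.
- *Haemoglobin.* 3 g/L is 0.3 g/dL, and 3/70 = 4.3%. In the text as it stands, the item requires haemolytic anaemia and a prednisone doubling, a prednisone increase to above 0.5 mg/kg/day, or hospitalisation. A small fall alone therefore triggers nothing. The protocol does not show that the value or unit is wrong.

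**The case for a change.** The strongest case for a change is that the protocol chose to fix this analysis rule and fixed only half of it: it says what these events are not, and omits what they are. The endpoint has two parts, any flare and severe flare, and the footnote settles the second in so many words but not the first. Under the literal reading, a participant measured against a score of 10 or more could never have a SLEDAI-only flare. Section 4.2 itself says that children tend to have higher activity scores than adults. In an open-label, single-arm study an event definition should be closed before the data are read, and the cost is one clause, with no new data collection.

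Part of this stands. No sentence says outright that the events remain flares, and a clause saying so would do no harm. The consequence does not stand, because it exists only under the reading that the footnote's own wording makes less likely. Turning a tick-box instrument into a dated event is also ordinary derivation work of the kind that a protocol leaves to the analysis plan.

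**Conclusion.** No change is needed. This is a missing detail that analysts fill sensibly: SLEDAI-only rises to above 12 are non-severe flares, counted in time to first flare and not in time to first severe flare. On that reading the number of lost events is zero.

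On the literal reading, the loss would be confined to events with no other trigger: no increase in prednisone, no added NSAID or hydroxychloroquine, none of the listed new immunosuppressants, no hospitalisation for SLE, no qualifying PGA rise and no listed new or worse manifestation. Section 6.5.1 allows treatment changes freely after Day 0, so a substantial worsening would often meet another row. The number affected cannot be derived from the protocol.

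The reach is also limited. This is one secondary endpoint in a study without a comparator, and Section 9.4.2.1 plans the consistency evaluation against BEL114055 for the primary efficacy endpoint. The primary endpoints and sample size do not depend on flares.

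The conclusion rests on two assumptions. First, the footnote is read by its ordinary sense. Second, the examples take the reference score to be near the entry level. If the reference is a lower score from an earlier visit, the mild-moderate row accepts more rises (from 4, rises of 3 to 8) and the literal gap narrows further. The PGA boundary is at most editorial. The minimum-change and haemoglobin points are not shown to be errors.
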